4.1. Overall Design

This will be a phase IV, open label, multicenter, randomized pragmatic study in frail elderly patients with COPD. Participants will be treated with either inhaled LABD alone or LABD combined with inhaled glucocorticosteroids. The choice of the specific LABD and ICS to be used will be left to the discretion of the clinical investigator, according to the treatments available from their pharmacy department.

The center will be considered as a unique stratifying factor, so the study will have a balanced-block center-stratified design.

The main aim of the study is to assess whether, in elderly patients with COPD and one or more cardiac comorbidities (heart failure, and/or ischemic heart disease, and/or atrial fibrillation) recently hospitalized because of an acute exacerbation of COPD, 12 months treatment with LABD(s)+ICS can increase the time to first re-hospitalization (all cause) and/or death for any cause when compared with LABD(s) alone. Patients will be followed-up for 3 months after completion of the 12 month treatment period.

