8.1.1. Assessment of re-hospitalizations and deaths (all cause)

Information on deaths (all cause) will be collected from the participant's medical records.

Information on re-hospitalizations (all cause) will be collected by reviewing the participant's medical records, from direct questioning of the participant during the follow-up visits and during monthly phone calls with the participant.

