8.1.4. Acute cardiac events

Acute cardiac events will be recorded based on the clinical evaluation.

Acute CV events are defined as an inpatient or emergency department visit with a primary diagnosis of any of the following conditions (International Classification of Diseases, 9th Revision, Clinical Modification (ICD-9-CM) codes are also shown). Coronary heart disease (ICD-9-CM codes 410-414), cardiac arrhythmia (ICD-9-CM code 427), heart failure (ICD-9-CM code 428), or ischemic stroke (ICD-9-CM codes 433-434) (Wang et al 2018).

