3.5 Efficacy endpoints

3.5.1 Primary endpoint

The primary efficacy endpoint is the time to first re-hospitalization and/or death (all cause).

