4.8 Changes in the planned analysis

The following changes were implemented in this SAP with respect to the analyses planned in the protocol:

- P-values of paired t-tests will not be provided for the mean change from baseline because the information is considered redundant with the one provided by the 95% confidence intervals.
- Vital signs and physical examination data will be listed only.

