7.1 Analysis of primary endpoint

Definitions and data conventions

First re-hospitalization and/or death

The event “first re-hospitalization and/or death” is identified as the first occurrence between the first re-hospitalization (as collected in the “COPD EXACERBATION FORM”) and death, if any of them occurred.

Time to first re-hospitalization and/or death

Forms			
Title		Statistical Analysis Plan Template	
Code		Version	Effective Date
FRM_ST03_032		02	02 Oct 2017
			17 of 26

In patients with at least one event, time to first re-hospitalization and/or death will be calculated as the weeks between baseline (Visit 2) and the date at which the first re-hospitalization (i.e., Date of admission/prolonged hospitalization in the ‘COPD Exacerbation Form’) and/or death occurs.

Time to first re-hospitalization and/or death (weeks) = (date of first re-hospitalization and/or death - Visit 2 + 1)/7

Patients without first re-hospitalization and/or death or who are discontinued before having it will be considered as “censored” at the end of the study visit (Visit 6) or at the time of the withdrawal during the treatment period (i.e., the date of withdrawal). For the analysis, the following formula will be applied:

Censoring time (weeks) = (date of Visit 6/withdrawal - Visit 2 + 1)/7

Time to first re-hospitalization and/or death for the sensitivity analysis.

The crossover occurrence is identified as patients that switch from one treatment group to the other adding or stopping ICS and it will be identified as protocol deviation.

In patients without the crossover occurrence , time to first re-hospitalization and/or death will be calculated as described above.

In patients with the crossover occurrence:

- if they experienced first re-hospitalization and/or death before or at the crossover occurrence date, time to first re-hospitalization and/or death will be calculated and considered as for the patients without the crossover occurrence;
- if they experienced first re-hospitalization and/or death after the crossover occurrence date, time to first re-hospitalization and/or death will be censored at the time of crossover occurrence;
- patients without first re-hospitalization and/or death will be considered as “censored” at the cross-over start date. For the analysis, the following formula will be applied:

Censoring time (weeks) = (date of cross-over start - Visit 2 + 1)/7

Primary efficacy analysis

Analysis will be performed on ITT population.

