7.2 Analysis of secondary efficacy endpoints

Definitions and data conventions

Number of re-hospitalizations and death

The number of re-hospitalizations and deaths will be calculated per-subject as the sum of the number of hospitalizations as recorded in the ‘COPD Exacerbation Form’ and the deaths (all cause).

Number of moderate/severe COPD exacerbations

The number of moderate/severe COPD exacerbations will be calculated per-subject as the sum of the number of COPD exacerbations recorded as “Moderate” or “Severe” in the ‘COPD Exacerbation Form’.

Number of pneumonia events

The number of pneumonia events will be calculated per-subject as the sum of adverse events classified with the following System Organ Classes/Preferred Terms:

System Organ Class	Preferred Term
Respiratory, thoracic and mediastinal disorders	
 • Pneumonia NOS • Acute pneumonia • Lung infection • Multilobar pneumonia • Bronchopneumonia • Pneumonia lobar • Pneumonia, organism unspecified • Bronchopneumonia NOS • Acute bronchopneumonia • Community acquired pneumonia • Lobar pneumonia NOS • Ventilator associated pneumonia • Healthcare associated pneumonia • Pneumonia recurrent • Bronchopulmonary infection

Forms			
Title	Statistical Analysis Plan Template		
Code	Version	Effective Date	Page
FRM_ST03_032	02	02 Oct 2017	20 of 26

	
 Pulmonary suppuration Lung infection NOS Pleuropneumonia Bronchopneumonia, organism unspecified Bilateral bronchopneumonia Infectious pneumonitis Nosocomial pneumonia Bronchial pneumonia Bilateral pneumonia Hospital acquired pneumonia Right middle lobe pneumonia Lobar pneumonia
--	---

Number of acute cardiac events

The number of acute cardiac events will be calculated per-subject as the sum of adverse events classified with the following System Organ Classes/Preferred Terms:

System Organ Class	Preferred Term
Cardiac disorders	
 Heart failures -Coronary artery disorders Cardiac arrhythmias Embolic stroke Haemorrhagic stroke Thrombotic stroke

Time on study

Time on study (years) will be calculated using the following formula:

Time on study (years) = (Date of patient completion or withdrawal - Date of randomization +1)/365.25.

Log-time on study (years)

The log-time on study in years will be calculated using the following formula:

$$\text{Log-time on study} = \ln(\text{time on study})$$

Statistical analysis

Analysis will be performed on the ITT population.

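### The SAP takes re-hospitalizations for the all-cause primary endpoint only from the COPD Exacerbation Form and does not declare this as a change

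*SAP*

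**What the plan says.** **Declared endpoint.** Protocol 4.1 sets the aim of showing that LABD(s)+ICS "can increase the time to first re-hospitalization (all cause) and/or death for any cause when compared with LABD(s) alone". SAP 3.5.1 repeats it: "The primary efficacy endpoint is the time to first re-hospitalization and/or death (all cause"). On ascertainment, Protocol 8.1.1 says "Information on re-hospitalizations (all cause) will be collected by reviewing the" participant's medical records, by direct questioning at visits and by monthly telephone calls. It names no disease-specific form.

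**Operational rule.** SAP 7.1 says the event is "identified as the first occurrence between the first re-hospitalization (as collected in the “COPD EXACERBATION FORM”) and death, if any of them occurred". It takes the event date from the admission/prolonged-hospitalization field of the same form. SAP 7.2 computes the secondary count as the "sum of the number of hospitalizations as recorded in the ‘COPD Exacerbation Form’ and the deaths (all cause"). Neither section names any other source of admissions.

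**Other events.** SAP 7.2 uses the COPD Exacerbation Form to count exacerbations graded moderate or severe. Cardiac events come from elsewhere: "The number of acute cardiac events will be calculated per-subject as the sum of adverse events" in listed MedDRA categories. Pneumonia is handled the same way.

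**Declared changes.** SAP 4.8 opens with "The following changes were implemented in this SAP with respect to the analyses planned in the protocol" and lists two items: paired t-test p-values are dropped, and vital signs and physical examination are listed only.

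**The concern.** The declared endpoint counts an admission for any reason. The rule a programmer would follow counts an admission only if it appears on a form named for, and used to grade, COPD exacerbations.

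Non-COPD admissions are foreseeable here. Every participant must have heart failure, ischemic heart disease or atrial fibrillation (Protocol 5.1), and the protocol calls comorbidities the most important risk factors for re-hospitalization. Protocol 8.1.4 expects such hospital contacts: "Acute CV events are defined as an inpatient or emergency department visit with a primary diagnosis of any of the following conditions", and goes on to list coronary disease, arrhythmia, heart failure and ischemic stroke.

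If those admissions are recorded elsewhere, a patient admitted for heart failure stays event-free in the primary analysis until a form-recorded admission, death or censoring. The trial would then test a narrower endpoint than the one it declares and sizes. The per-protocol, crossover and triple-therapy analyses use the same event definition, so none of them would reveal the gap.

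**Working it through.** **1. Sources side by side**

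| Item | Declared | SAP source |
|---|---|---|
| Re-hospitalization, occurrence | All cause (Protocol 4.1, 8.1.1; SAP 3.5.1) | COPD Exacerbation Form (SAP 7.1) |
| Re-hospitalization, date | Not specified | COPD Exacerbation Form (SAP 7.1) |
| Re-hospitalization, number | All cause (SAP 3.5.2) | COPD Exacerbation Form (SAP 7.2) |
| Death | All cause | Any death |
| Acute cardiac events, pneumonia | Separate secondary endpoints | Adverse events (SAP 7.2) |
| Change from protocol | – | Not among the two in SAP 4.8 |

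**2. The plan's own sample size**

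Inputs (Protocol 9.2, SAP 3.3): 464 per group, 15% of LABD and 9% of LABD+ICS patients with the composite event, two-sided 5% log-rank test, 80% power.

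- HR = ln(1 − 0.09)/ln(1 − 0.15) = 0.580
- Expected events = 464 × (0.15 + 0.09) = 111.4
- Freedman power = Φ(√events × (1 − HR)/(1 + HR) − 1.96) = Φ(2.803 − 1.96) = 80.0%

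In the other direction, Freedman's formula needs 112 events, so 112/0.24 = 467 per group, close to 464. The dropout figure also follows: 464/0.9 = 516. The stated sample size is not in dispute.

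**3. If the form misses some admissions**

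The documents give no capture share, so every row below the first is an assumption. The same formulas are applied with 464 per group. In (a), the HR is held at 0.580 and only the number of events falls. In (b) and (c), percentage points are removed from each arm and the HR is recomputed.

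| Scenario | LABD vs LABD+ICS | HR | Events | Power |
|---|---|---|---|---|
| As planned | 15% vs 9% | 0.580 | 111.4 | 80.0% |
| (a) 70% of events captured | – | 0.580 | 78.0 | 65% |
| (a) 50% of events captured | – | 0.580 | 55.7 | 51% |
| (b) 2 points lost per arm | 13% vs 7% | 0.521 | 92.8 | 86% |
| (b) 3 points lost per arm | 12% vs 6% | 0.484 | 83.5 | 89% |
| (b) 4 points lost per arm | 11% vs 5% | 0.440 | 74.2 | 92% |
| (b) 5 points lost per arm | 10% vs 4% | 0.387 | 65.0 | 94.5% |
| (c) 5 points lost from LABD, 2 from LABD+ICS | 10% vs 7% | 0.689 | 78.9 | 37% |
| (c) 2 points lost from LABD, 3 from LABD+ICS | 13% vs 6% | 0.444 | 88.2 | 95% |

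Scaling both event percentages by the capture share, instead of fixing the HR, gives 63% at 70% capture and 48% at 50% capture, close to (a).

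Power falls if the lost events carry the same relative effect as the rest. It rises if they carry no treatment effect, as in (b). Both the estimate and the power can therefore move either way.

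**The case against.** The strongest objection is that the harm depends on a CRF nobody here can see. A form's name does not fix its content, and the SAP authors worked from the CRF. Some cues fit a single all-purpose form:

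- The schedule of activities combines symptoms and hospitalizations in one row.
- The date field resembles the general seriousness criterion (admission or prolongation).
- SAP 7.2 counts hospitalizations on the form separately from graded exacerbations.

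Silence in SAP 4.8 also fits a case where no restriction was intended, and one admission could be both an adverse event and a form entry. Some admissions with worsening respiratory symptoms could properly be entered as exacerbations under Protocol 8.1.2.

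This stands to the extent that a narrower endpoint is not proven. It does not remove the problem. No cue shows that the form takes admissions of any cause, and the SAP nowhere says that it does. As written, the rule ties occurrence, date and number to that form alone.

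Two further points are fair. First, the power scenarios are illustrations and measure no actual loss. Second, the background does not settle direction: the protocol introduction links ICS to pneumonia risk, reports no or marginal risk in some recent trials, and cites a reduction in some cardiovascular events in one.

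**Conclusion.** The concern holds and must be fixed before analysis. The declared primary endpoint and its derivation rule do not match, and SAP 4.8 does not disclose the difference. The same mismatch affects the secondary count of re-hospitalizations and deaths.

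Whether admissions are actually lost depends on one unverified condition: that sites do not enter every admission on the COPD Exacerbation Form. Only the hospitalization component is affected. If the condition is met, the trial tests a different endpoint from the one declared and sized at 15% vs 9%.

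The effect on power cannot be determined from the documents. Against a planned 80%, the assumed scenarios run from about 37% to about 95%. The firm conclusion is that the endpoint as derived may not be the all-cause endpoint as declared; a loss of power is not established.

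**What to change.** In SAP 7.1 (earliest admission) and SAP 7.2 (all admissions), derive re-hospitalization from every recorded source:

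- hospitalization data from visits and monthly calls;
- AE/SAE records meeting the hospitalization criterion;
- hospitalizations that Protocol Appendix 3 has recorded in the CRF without SAE handling;
- the COPD Exacerbation Form.

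De-duplicate by admission date. State in advance whether the elective, pre-planned and routine admissions described in Appendix 3 count. Keep COPD-exacerbation admission or death as a labelled supportive analysis.

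If the form already holds every admission whatever its cause, say so in 7.1 and 7.2 and reconcile it against the SAE records before analysis. If a restriction is intended, declare it in SAP 4.8 and stop describing the hospitalization component as all-cause.

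**Cost.** SAP wording, plus derivation and reconciliation work. The protocol already has hospitalizations recorded on the eCRF (8.1), SAEs in the CRF (8.3.4) and non-SAE hospitalizations in the CRF (Appendix 3), so no new assessments of patients are needed. If admission dates turn out to be held only on the COPD form or on the paper SAE forms, some dates would have to be retrieved from existing records. The sample size of 464 (516 randomized) per group does not change.

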9.4.6. Efficacy Analyses

Primary Efficacy Variable

The primary efficacy variable is the time from baseline (Visit 2) to first re-hospitalization and/or death. If the patient discontinues/completes the treatment period and no re-hospitalization and/or death is observed, then the time to first re-hospitalization and/or death is treated as right censored at the end of treatment period (i.e. date of Visit 6) or at the time of the withdrawal during the treatment period (i.e. the date of discontinuation).

The primary efficacy variable will be analyzed using the Kaplan-Meier estimator. Comparison between treatment groups will be performed using the log-rank test stratified by center. A Kaplan-Meier plot for time to first re-hospitalization and/or death will also be presented by treatment group.

The LABD(s)+ICS group will be declared to prolong time to first re-hospitalization and/or death, compared to the LABD(s) group, if the difference between the two treatments is significantly in favour of LABD(s)+ICS (i.e. the p-value from the log-rank test is ≤ 0.050).

In addition, a Cox proportional hazards regression analysis will be performed as well, presenting the treatment effect as a hazard ratio with the associated 95% confidence interval with center, age and treatment group as factors. The inclusion of any other potential confounding factors in the model will be evaluated during the Data Review, verifying the homogeneity of factors distributions among treatment groups.

A sensitivity analysis will be also carried out excluding efficacy data (i.e. hospitalization and death) collected after the crossover occurrence (i.e. patients that switch from one treatment group to the other adding or stopping ICS). The crossover patients that do not experience any hospitalization or death will be considered as censored at the time of cross-over start. Kaplan-Meier, log-rank test and Cox model will be repeated on this modified analysis dataset.

Secondary Efficacy Variables

The number of re-hospitalizations and deaths (all cause) will be analysed using a Poisson regression model. The model will include the number of events as dependent variable and treatment group, age and center as factors. Log-time on study will be used as an offset. The over dispersion parameter based on the deviance will be considered in order to account for between-patient variability in the events rate and standard errors will be estimated allowing for extra-Poisson variation.

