2.1 Primary objective

The primary objective is to demonstrate that in elderly Chronic Obstructive Pulmonary Disease (COPD) patients with one or more cardiac comorbidities (heart failure, and/or ischemic heart disease, and/or atrial fibrillation) who have been recently hospitalized due to an Acute Exacerbation of Chronic Obstructive Pulmonary Disease (AECOPD), 1-years treatment with Long-Acting Beta2-Agonist (LABD)+ Inhaled Glucocorticosteroids (ICS) will prolong the time to first re-hospitalization and/or the death for any cause when compared to 1-years treatment with LABD alone.

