Time to first re-hospitalization and/or death will be analysed using the Kaplan-Meier estimator. The number of re-hospitalization and/or death-free patients at the beginning of the period, the cumulative number of patients with re-hospitalization and/or death at the end of the period and the probability of being re-hospitalization and/or death-free at the end of the period with the associate 95% CIs will be presented by treatment for the following study periods: (0-12] weeks, (12-24] weeks, (24-36] weeks and (36 weeks-EoT]. The point estimates and the relative 95% CIs will be

Forms			
Title	Statistical Analysis Plan Template		
Code	Version	Effective Date	Page
FRM_ST03_032	02	02 Oct 2017	18 of 26

presented by treatment for the 75th, 50th and 25th percentiles. Comparison between treatments will be performed using the log-rank test stratified by center.

The LABD(s)+ICS group will be declared to prolong time to first re-hospitalization and/or death, compared to the LABD(s) group, if the difference between the two treatments is significantly in favour of LABD(s)+ICS (i.e., the p-value from the log-rank test is ≤ 0.050).

Plots of first re-hospitalization and/or death-free survival by treatment will also be presented.

The following SAS[®] code will be used to provide the Kaplan-Meier estimates for time to first re-hospitalization and/or death:

```
proc lifetest data=dataset TIMELIST=(12 24 36 EOT_A, EOT_B);
time TIME*EVENT(1);
strata CENTER / group=TMT;
run;
```

where TIME represents the time to first re-hospitalization and/or death or time to censoring, EVENT the censoring indicator (1 = censored patient), CENTER the center and TMT the treatment group; EOT_A, EOT_B, have to be replaced by the last time to first re-hospitalization and/or death or last time before EOT for each treatment group (if any).

Time to first re-hospitalization and/or death will also be analyzed using a Cox proportional hazards regression analysis with center and treatment group as qualitative independent variables and age as quantitative independent variables. The inclusion of any other potential confounding factors in the model will be evaluated during the Data Review, verifying the homogeneity of factors distributions among treatment groups.

The number of patients and the number of patients considered in the model will be provided by treatment. P-values of the independent variables based on Wald chi-square test will also be presented.

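### SAP 7.1 sets no last date for a completer's first event, although event-free completers are censored at Visit 6; programmed as written, the Kaplan-Meier tail is an artefact and the hazard ratio moves modestly towards 1

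*SAP*

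**What the plan says.** **Event rule, SAP 7.1.** "In patients with at least one event, time to first re-hospitalization and/or death will be calculated as the weeks between baseline (Visit 2") and the first admission or death. No latest date is given.

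**Censoring rule, SAP 7.1.** "Patients without first re-hospitalization and/or death or who are discontinued before having it will be considered as" censored, at Visit 6 or at withdrawal during treatment. Discontinued patients therefore have a limit. A completer whose first event falls after Visit 6 is neither event-free nor discontinued, and no limit is stated for that patient.

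**Crossover analysis, SAP 7.1.** Here late events are dealt with in terms: "if they experienced first re-hospitalization and/or death after the crossover occurrence date, time to first re-hospitalization and/or death will be censored at the time" when the switch took place. Patients who do not cross over keep the main rule.

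**Kaplan-Meier output, SAP 7.1.** The last tabulated period ends at EoT. The placeholders EOT_A and EOT_B "have to be replaced by the last time to first re-hospitalization and/or death or last time before EOT for each treatment group". The plot has no stated right-hand limit.

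**Protocol 9.4.6.** "If the patient discontinues/completes the treatment period and no re-hospitalization and/or death is observed", the time "is treated as right censored at the end of treatment period (i.e. date of Visit 6"), or at discontinuation. Status is thus judged at the end of the treatment period.

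**SAP 4.8.** Under "The following changes were implemented in this SAP with respect to the analyses planned in the protocol" it lists two items: paired t-test p-values are dropped, and vital signs and physical examination are listed only. The event window is not among them.

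**Data collection.** The Schedule of Activities and the Visit 7 description in Protocol section 8 continue the collection of hospitalizations and serious adverse events to three months after Visit 6.

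**The concern.** The event rule and the censoring rule stop at different dates for the same kind of patient. A completer first admitted in month 14 becomes an event at about week 61 (14 x 30.44 / 7). A completer with no event leaves the risk set at about week 52. Whether a patient stays at risk after Visit 6 then depends on whether that patient will later have an event.

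At stake are the plotted curve, the 25th, 50th and 75th percentiles that SAP 7.1 asks for, and the reported hazard ratio. The EoT row of the table is affected only if EOT_A or EOT_B is set to a time after Visit 6. The triple-therapy subgroup, and the non-crossover patients in the crossover analysis, inherit the same event time. The trial is open-label, so the primary event window should not be left to a programming choice.

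**Working it through.** **1. Inputs.** From SAP 3.3 and Protocol 9.2: 15% and 9% with an event, 464 per group, two-sided 5%, 80% power, 10% dropout. From the Protocol synopsis: 39 centers. Assumed, because the documents do not give them: constant hazards with the two rates read as yearly rates, Visit 6 near day 365 (SD 5 to 15 days), Visit 7 91 days later, and every late first event captured.

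**2. The plan's own figure.** HR = ln(0.91)/ln(0.85) = 0.580. Freedman events = (1.960 + 0.842)² x (1.580/0.420)² = 111.3. Per group: 111.3 / 0.12 / 2 = 463.7, so 464; 464/0.9 gives 516. The figures reproduce. Expected events: 464 x 0.15 + 464 x 0.09 = 69.6 + 41.8 = 111.4.

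**3. First events between Visit 6 and Visit 7.** Yearly hazards are 0.1625 and 0.0943.
- LABD: 464 x 0.85 x (1 - exp(-0.1625/4)) = 15.7.
- LABD+ICS, effect continues: 464 x 0.91 x (1 - exp(-0.0943/4)) = 9.8. Total 25.5, about 26.
- LABD+ICS, effect stops: 464 x 0.91 x (1 - exp(-0.1625/4)) = 16.8. Total 32.5, about 33.

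The event count rises from 111 to about 137 or 144.

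**4. Why the curve falls to 0.** Suppose every Visit 6 is on day 365. Just afterwards the LABD risk set is the roughly 16 patients with a late event and nobody else. After j of them, the estimate is 0.85 x (16 - j)/16. It passes 0.75 at j = 2 (0.744) and 0.50 at j = 7 (0.478), and reaches 0 at j = 16. The true 15-month value is 0.85 x exp(-0.1625/4) = 0.816. At a 15% yearly rate the true 25th percentile is ln(0.75)/ln(0.85) x 365.25/7 = 92.4 weeks, which is beyond follow-up.

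**5. Simulated curves with Visit 6 spread (SD 5 to 15 days).**
- Day 365, events cut at Visit 6 against SAP as written: LABD 0.849-0.851 against 0.846-0.849; LABD+ICS 0.909-0.911 against 0.906-0.910.
- Day 400, as written: 0.57-0.73 and 0.62-0.81.
- Last event, as written: about 0.00 in both arms at weeks 64-66. With the cut, the curves end at about 0.84 and 0.90-0.91.
- 25th/50th/75th percentiles as written: about 55-57/58-60/62-63 weeks (LABD) and 56-59/59-61/62-63 weeks (LABD+ICS). With the cut, the 25th percentile is not reached in 97% to 100% of trials.

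**6. Simulated hazard ratio (treatment-only Cox) and stratified log-rank power.** 600 trials per row, 39 centers; Monte Carlo SE of power about 0.016.

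| Effect after Visit 6 | Visit 6 SD (days) | HR, cut at Visit 6 | HR, SAP as written | HR, events and censoring both to Visit 7 | Power, cut / as written |
|---|---|---|---|---|---|
| continues | 5 | 0.576 | 0.623 | 0.577 | 0.812 / 0.812 |
| continues | 10 | 0.589 | 0.627 | 0.588 | 0.763 / 0.777 |
| continues | 15 | 0.577 | 0.609 | 0.578 | 0.800 / 0.820 |
| stops | 5 | 0.572 | 0.643 | 0.654 | 0.818 / 0.803 |
| stops | 10 | 0.576 | 0.649 | 0.656 | 0.823 / 0.782 |
| stops | 15 | 0.579 | 0.647 | 0.663 | 0.808 / 0.760 |

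The two rules give the same significance decision in 95-98% of trials if the effect continues and 91-95% if it stops.

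**7. Cox model with center and age, as SAP 7.1 specifies.** At SD 10 (120 trials) the paired shift in log HR is 0.035 or 0.100. This gives 0.58 x exp(0.035) = 0.60, or 0.58 x exp(0.100) = 0.64. A separate run of 150 trials gave 0.600 and 0.628. Against a standard error of 0.198 the shifts are 0.18 and 0.51 SE. With center only and a fixed Visit 6 date (800 trials), 0.570 became 0.608 and 0.563 became 0.613. Log-rank power there went from 0.804 to 0.787 and from 0.836 to 0.815.

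**8. Why the primary test barely moves.** Late events average 25.5/39 = 0.65 per center, or 32.5/39 = 0.83. A center with one patient left at risk adds nothing to a center-stratified log-rank statistic. The Cox model pools all centers in one risk set, so it is affected more.

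**The case against.** The strongest reply is that the intended window can be recovered. SAP 7.1 treats Visit 6 as the final visit, SAP 5.3 uses its date when the completion date is missing, the last Kaplan-Meier period ends at EoT, and SAP 2.1 asks whether one year of LABD+ICS "will prolong the time to first re-hospitalization and/or the death for any cause when compared to 1-years treatment with LABD alone". A careful programmer may well apply the limit unprompted. This stands as evidence of intent. It does not supply the missing rule, and Protocol 4.4 defines study completion at Visit 7, which points the other way.

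Three further limits stand.
- SAP 7.1 takes admissions from the COPD Exacerbation Form, and the documents do not say whether that form is completed after Visit 6. Deaths do not depend on it. The counts of 26 and 33 assume full capture; fewer captured events mean a smaller shift.
- Protocol 6.7 says patients stay on treatment, although prescribing becomes discretionary. The case where the effect stops at Visit 6 is therefore an upper bound.
- The artefact begins after week 52, where a reader of a 12-month analysis may notice it.

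Stronger readings are tempting but unsupported. A reader might infer that late events are capped only for crossover; discontinued patients are also censored, at withdrawal. A reader might take the 111 planned events as proof of a 12-month window; the 15% and 9% carry no time window in the sample-size text. A reader might infer that the SAP deliberately moved to a 15-month endpoint; event-free patients are still censored at Visit 6, and SAP 4.8 declares no such change.

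**Conclusion.** The gap is real and is confined to completers whose first event falls between Visit 6 and Visit 7. Followed as written, SAP 7.1 gives curves that end at about 0 in both arms and, at the planned rates, percentile values that should be reported as not reached. The drop to 0 needs only that late events are counted. At the 30% yearly rate mentioned in Protocol 2.3, the LABD 25th percentile (ln(0.75)/ln(0.70) x 365.25/7 = 42.1 weeks) would be genuine, and only the later percentiles would be artefacts.

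The hazard-ratio shift is modest and rests on the assumptions in step 1. Treatment-only, it is from about 0.58 to 0.61-0.63 if the effect continues and to 0.64-0.65 as an upper bound. The upper-bound shift is largely dilution, since a consistent 15-month analysis gives 0.65-0.66. With center and age it is to about 0.60, or 0.63-0.64.

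A reader might conclude that the primary test is invalid or that its result could be reversed. The figures do not support that. Stratified log-rank power changes by at most about 0.02 either way if the effect continues and falls by 0.02 to 0.05 if it stops, and estimates up to Visit 6 are essentially unchanged. The point should be fixed before programming, but it does not threaten the trial's conclusion.

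**What to change.** In SAP 7.1:
- State that only events dated on or before the earlier of Visit 6 and withdrawal count, and that a completer whose first event is later is censored at Visit 6, consistent with Protocol 9.4.6.
- State that EOT_A and EOT_B may not exceed Visit 6.
- Apply the same limit to the crossover analysis and the triple-therapy subgroup.
- Report events between Visit 6 and Visit 7 separately. If a 15-month comparison is wanted, label it as such and follow event-free patients to Visit 7 as well.

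The cost is one sentence, one limit on the EOT values and a date filter in the programs. On the window that the protocol implies, no primary events are lost.
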